## 8.2 SAFETY AND OTHER ASSESSMENTS

- The bi-weekly phone encounters and EMR reviews are the primary means of monitoring the occurrences of side effects and participant tolerability of the Gentamicin treatment. If a participant reports a UTI or UTI symptoms, they will be advised to follow-up with their personal provider for management. Any potential manifestation of gentamicin toxicity will also be assessed during these phone encounters. These include new onset and prolonged numbness, skin tingling, dizziness, and vertigo. They also include prolonged muscle twitching, tinnitus, roaring in the ears or hearing loss. The study team will recommend subjects with these symptoms be seen by a physician for otological assessment and possible study treatment discontinuation.
- A complete blood count and comprehensive metabolic panel will be administered at baseline and six months when treatment is concluded.
- If a study-ordered urine analysis (at screening, and approximately 6-months later, defined here with a window of plus or minus 30 days) reveals an infection, participants will be instructed to follow-up with their personal provider to treat the current infection. The results of the urine test will be included in the EMR and be available to providers across institutions with EPIC access.
- During the follow-up interview (3-months post-treatment), the participant will also be asked if they have used any gentamicin instillations since being off the study drug. If they have used gentamicin, they will be asked if they are still using it. If they have not used gentamicin, they will be asked why not.

- After the follow-up interview, participants will be thanked for their participation in the trial and asked to participate in a final optional survey. If willing, they will be asked about their perceptions of the benefits and/or challenges of using Gentamicin instillations and whether they thought their participation in this trial was worthwhile. This information will be recorded in their CRFs. This option will be offered to participants at the end of their 3-months post-treatment interview and/or at a different time following this interview, depending on their availability and interest in participating.

## 8.3 ADVERSE EVENTS AND SERIOUS ADVERSE EVENTS

### 8.3.1 DEFINITION OF ADVERSE EVENTS (AE)

This study's definition of AE will align with the FDA definition: "any untoward medical occurrence associated with the use of a drug in humans, whether or not considered drug related." In practice, this means we will consider and document any experience or unfavorable and unintended sign, symptom, or disease that arises while an individual is participating in the study. This interpretation includes positive test results on urine analysis and urine culture (both those provided by the study and those ordered by the participant's treating physician) and reports of UTI symptoms (e.g., malodorous and cloudy urine, fatigue, fever, chills, etc.)

### 8.3.2 DEFINITION OF SERIOUS ADVERSE EVENTS (SAE)

Similarly, this study will use the FDA definition of SAE:

"An adverse event or suspected adverse reaction is **considered "serious"** if, in the view of either **the investigator or sponsor**, it results in any of the following outcomes: **Death, a life-threatening adverse event, inpatient hospitalization or prolongation of existing hospitalization, a persistent or significant incapacity or substantial disruption of the ability to conduct normal life functions, or a congenital anomaly/birth defect.**"

This definition goes on to **include any other "important medical events"** that may not result in death, be life-threatening, or require hospitalization, but may be considered serious when deemed as such by medical judgment. These **events may jeopardize the participant and may require medical or surgical intervention to prevent one of the outcomes listed above.** Examples of such medical events include hospitalization for complications from a UTI (e.g., kidney infection, sepsis), allergic response requiring intensive treatment, other side effects or complications that require intensive or ongoing treatment and/or admission to the hospital.

AE occurrences can be caused by any of the study products themselves, other aspects of the interventions like reactions to the catheter supplies, research procedures, the underlying health status of the participant, and any concurrent treatments or therapies not necessarily associated with the study. There might be other causes of AEs that we haven't considered.

### 8.3.3 CLASSIFICATION OF AN ADVERSE EVENT

The PI, and Co-Is [name] and [name] will be the final arbiters of AE classification.

#### 8.3.3.1 SEVERITY OF EVENT

This study will classify adverse events using the Common Terminology Criteria for Adverse Events (CTCAE) v4.0 from 2009:

- Grade 1 - Mild; asymptomatic or mild symptoms; clinical or diagnostic observations only; intervention not indicated.
- Grade 2 - Moderate; minimal, local or noninvasive intervention indicated; limiting age-appropriate instrumental ADL; impact on ADLs will be considered within the context of the individual participant's usual capacity.
- Grade 3 - Severe or medically significant but not immediately life-threatening; hospitalization or prolongation of hospitalization indicated; disabling; limiting self-care ADL\*.
- Grade 4 - Life-threatening consequences; urgent intervention indicated.
- Grade 5 - Death related to AE.

Under this classification system, UTIs are a "disorder characterized by an infectious process involving the urinary tract, most commonly the bladder or the urethra." The severity classification begins with grade 2:

- Grade 2 - Localized; local intervention indicated (e.g., topical antibiotic, antifungal, or antiviral)
- Grade 3 - IV antibiotic, antifungal, or antiviral intervention indicated; radiologic or operative intervention indicated.
- Grade 4 - Life-threatening consequences; urgent intervention indicated.
- Grade 5 - Death

#### 8.3.3.2 RELATIONSHIP TO STUDY INTERVENTION

##### DEFINITELY RELATED

- The event is a known effect of the drug, or procedure (e.g., listed in the protocol documents, consent, publications).
- The event follows an obvious sequence of time, from the drug's administration, or procedure, for which the event is directly attributed to the administration, implantation, activation, or procedure.
- The event ceases with discontinuation of the drug, or procedure (and reoccurs on restarting).
- The event includes data that was only collected for the study.
- The event included disturbing or upsetting questions that the subject was asked for the purpose of the research.

##### PROBABLY RELATED

- The event is a lesser known or suspected effect of the drug, or procedure (listed in the protocol documents including consent, publications, etc.)
- The event follows a reasonable sequence of time from the drug's administration, or procedure, for which the event may be attributed to the administration, or procedure.
- The event ceases or diminishes with discontinuation of the drug, or procedure.

#### POSSIBLE RELATED

- The event is a lesser known or possible effect of the drug, or procedure.
- The event occurred within a sequence of time from the drug's administration, or procedure, for which the event may be attributed to the administration or procedure.
- The event could be explained by the characteristics of the population under study.

#### UNLIKELY RELATED

- The event is NOT a previously known or suspected effect of the test drug, or procedure.
- The event does NOT follow a sequence of time from drug administration, or procedure, for which the event could be attributed to the administration, or procedure.
- The event can be readily explained by the characteristics of the population under study.

#### NOT RELATED

- The event is NOT known to be an effect of the test drug, or procedure.
- The event does NOT follow a sequence of time from drug administration, or procedure, for which the event could be attributed to the administration, implantation, activation, or procedure.
- The event can be readily and easily explained by the characteristics of the population under study.
- Subject never received study drug or underwent research study procedure.

#### 8.3.3.3 EXPECTEDNESS

The determination of expectedness is assessed based on the awareness of AEs previously observed, not on the basis of what might be anticipated from the properties of the study intervention. An AE will be considered "expected" if any of the following conditions are met:

- The event is listed on the informed consent document.
- The event is documented in the proposal to the National Institute on Disability, Independent Living and Rehabilitation Research, this protocol document or IRB application.
- The event is listed as a side effect in the respective drug information materials for gentamicin and saline.
- The event is identified in published literature or otherwise related to the study population (for example, UTIs would be expected, pressure sores would be expected, heart attack would not necessarily be expected given the characteristics of the study population, etc.).

---

#### 8.3.4 TIME PERIOD AND FREQUENCY FOR EVENT ASSESSMENT AND FOLLOW-UP

- Study staff will call or otherwise contact participants and/or their caregivers to assess for side effects, adverse events, UTI symptoms, etc. every two weeks for the duration of the study intervention.
  - Staff will ask about changes in health status since enrollment in the study.
  - Study staff will ask directed questions regarding specific side effects or difficulties related to the bladder instillation.
- The reporting period for AEs will begin when the participant signs the main consent and end 30 days after the end of treatment.

---

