*Fetal Harm* – Aminoglycosides such as gentamicin can cause fetal harm when administered to pregnant women. A pregnancy test will be administered to females of child-bearing potential at screening. Sexually active females of child-bearing age will also be asked to use appropriate contraception throughout the study while on the study treatment. Subjects who become pregnant after enrollment will be asked to discontinue the study treatment, but may remain in the study, tracking their UTIs and completing study interviews.

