### 5.3 LIFESTYLE CONSIDERATIONS

Participants should show indications of health seeking behaviors (i.e. following bladder management procedures), and be able to consult with their personal physicians when noticing symptoms related to bladder complications and/or UTIs. They should have access to caregivers or family members, as needed, to assist them with instillations following regular catheterizations. Healthy behaviors related to hygiene when having to catheterize and during bowel management procedures are also important.

During this study, the management of all ongoing and new bladder or bowel issues will continue to fall under the purview of the participant's treating physician or care provider. The study team will not offer treatment for any new-onset UTIs, in their role on the study. This means that participants are expected to contact their provider about any new symptoms or infections. Since the physicians on the study team also provide treatment to SCI/D patients for urinary issues, in this clinician role, they may provide participants with care.

Participants or their assistants should be willing to follow study protocol for storage of the medication and preparation of dose for daily instillations as well as complete their dosing diaries.

Dietary restrictions and activity limitations are not required for participants while they are enrolled in this study. Should a participant start one of the contraindicated diuretics above, or become pregnant, they will discontinue the study treatment and notify the study team. Female participants will be asked about pregnancy and compliance with the use of contraception during their bi-weekly follow up visits.

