## 7 STUDY INTERVENTION DISCONTINUATION AND PARTICIPANT DISCONTINUATION/WITHDRAWAL

### 7.1 DISCONTINUATION OF STUDY INTERVENTION

Participants may elect to discontinue the study intervention for any number of reasons (not inclusive list): burden of study procedures, side effects, caregiver limitations, etc. They will be educated on signs and symptoms of toxicity (see Section 8.2) and instructed to notify the study team and their physician for advice on discontinuation of study treatment. If a participant develops COVID-19 while participating in this study, the study team will make every effort to keep the participant in the trial. Participants with COVID-19 will remain in the study unless, for medical reasons, they can no longer participate.

Participants will be asked about the reasons for withdrawal from the study when self-initiated.

Regardless of the reason, discontinuation of the study treatment does not mean withdrawal from the study since the study uses an intent –to-treat design. If a participant decides to stop using the study product, and they are willing, they will remain enrolled in the study. This means that study procedures, including bi-weekly phone calls and study visits will go on as scheduled. No drug taper is required when subjects discontinue the study treatment – they may stop immediately. These subjects will also complete the study's final assessments, if willing.

Regarding the discontinuation of treatment, the following information will be documented in the study record:

- Reason for discontinuation of intervention (i.e. treatment).
- Date of last dose.
- Willingness to continue in the study.

If a participant decides to discontinue the study intervention in light of a new or exacerbated clinical finding, we will report the finding on the Adverse Event case report form, and report to the necessary entities as outlined in the Events Reporting Schedule.

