### 7.2 PARTICIPANT DISCONTINUATION/WITHDRAWAL FROM THE STUDY

Participants may withdraw from the study at any time; likewise, the study team can withdraw a participant from the study given any of the following reasons:

- Individual expresses desire to stop participation.
- A new or exacerbated clinical occurrence or adverse event that precludes safe and meaningful participation in the remaining study activities (note: while it may be necessary for a participant who experiences an adverse event to discontinue study treatment, they do not necessarily need to be withdrawn from the study).

- This criterion can include, but is not limited to, an adverse event, disease progression, other medical condition or lab finding.
- Individual fails to comply with study requirements (e.g., unable or unwilling to complete lab exams, outcome assessments, lost-to-follow up, maintain appropriate communications with the study team, etc.)
- Study team discretion that continued participation is unlikely to be safe and/or meaningful.
- Participant status changes such that an individual no longer meets eligibility criteria.

The reason for withdrawal will be documented in the study record (i.e., CRFs and REDCap database). Participants will be informed that they have been withdrawn from the study by the study team.

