### 8.3.9 REPORTING OF PREGNANCY

Pregnancy is not considered an adverse event, but it is an exclusion criterion for the study. Individuals reporting a new pregnancy will discontinue their study intervention and will be withdrawn from the study.

---

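### Section 2.3.1 lets a participant who becomes pregnant stay in the study, but section 8.3.9 withdraws her; 8.3.9 should be aligned so that her follow-up is kept

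*Protocol*

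**What the plan says.** The protocol treats pregnancy on study drug in several places.

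- Section 2.3.1 names the risk: "Aminoglycosides such as gentamicin can cause fetal harm when administered to pregnant women". It then sets the handling: "Subjects who become pregnant after enrollment will be asked to discontinue the study treatment, but may remain in the study", with UTI tracking and interviews continuing.
- Section 5.3 says that if participants start a prohibited diuretic "or become pregnant, they will discontinue the study treatment and notify the study team". It is silent on staying or leaving. It also has female participants asked about pregnancy at the bi-weekly contacts.
- Section 7.1 gives the general rule: "discontinuation of the study treatment does not mean withdrawal from the study". Calls and visits carry on for those who are willing.
- Section 7.2 is permissive: "the study team can withdraw a participant from the study given any of the following reasons". Loss of eligibility is one of the reasons listed.
- Section 8.3.9 declares that pregnancy is not an adverse event, calls it an exclusion criterion, and directs: "Individuals reporting a new pregnancy will discontinue their study intervention and will be withdrawn from the study".

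On safety reporting, section 8.3.2 closes its list of serious outcomes with "or a congenital anomaly/birth defect". Section 8.3.4 sets the collection period: "The reporting period for AEs will begin when the participant signs the main consent and end 30 days after the end of treatment". Section 8.3.6 requires SAEs to be reported and followed to resolution, and gives no closing date. The SAP does not mention pregnancy.

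**The concern.** A coordinator who learns of a pregnancy at a bi-weekly call has two current instructions that cannot both be carried out. The choice has consequences. If 8.3.9 is followed, the participant with the exposure that the protocol itself flags as hazardous loses the scheduled contacts that every other participant who stops treatment would keep. Her remaining UTI and quality-of-life data are also lost to the intent-to-treat analyses of section 9.3.

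There is a related, weaker question. The protocol names fetal harm and makes a birth defect a serious outcome, yet the text available here contains no step that asks how an exposed pregnancy ended. At stake is whether one rare but serious outcome would be found at all.

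**Working it through.** **Step 1: can the two instructions be reconciled?**

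| Section | Study drug | Study participation |
|---|---|---|
| 2.3.1 | stop | may stay |
| 5.3 | stop, notify team | not stated |
| 7.1 (any reason for stopping) | stop | stays if willing |
| 7.2 (no longer eligible) | – | team may withdraw |
| 8.3.9 | stop | withdrawn |

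Section 8.3.9 cannot be read as withdrawal from the drug only, because it lists stopping the intervention and leaving the study as two separate actions. Section 7.2 allows withdrawal but does not require it. Only 8.3.9 makes it mandatory. All of this is current text, not the amendment history.

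**Step 2: what does following 8.3.9 remove?** Under 7.1, a participant who stops but stays keeps the bi-weekly calls, Visit 2 and Visit 3. Section 1.3 schedules record review and clinical history at both visits. Section 8.1 adds record review every two weeks and an update of health status at each interview. Once she is withdrawn, none of these clearly applies.

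**Step 3: when does routine AE collection close, relative to a term birth?** The plan gives no figure of its own to reproduce.

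Inputs from the protocol, with day 0 as the first instillation:
- treatment lasts six months from the first instillation (6.1.1), and six months means 180 days (1.1, footnote);
- AE collection ends 30 days after treatment (8.3.4).

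Input assumed, because the documents give none: 266 days from conception to term (40 weeks' gestation). The check at 37 weeks uses 245 days.

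Full 180-day course:
- window closes: 180 + 30 = day 210;
- term birth, conception on day 0: 0 + 266 = day 266, so the gap is 266 − 210 = 56 days;
- term birth, conception on day 180: 180 + 266 = day 446, so the gap is 446 − 210 = 236 days.

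If the 30 days run from the day she stops, let s be the days from conception to last dose (0 to 180):
- gap = 266 − (s + 30) = 236 − s, which is again 56 to 236 days;
- for example, stopping 28 days after conception gives 236 − 28 = 208 days.

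Sensitivity:
- birth at 37 weeks: 245 − 210 = 35 days at the least;
- treatment stretched to day 210, the upper edge of the Visit 2 window but not a planned course: closure on day 240, so gaps of 266 − 240 = 26 days at 40 weeks and 245 − 240 = 5 days at 37 weeks.

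Limits: the result covers term births conceived on treatment. A miscarriage or preterm birth could fall inside the window. So could a birth from a conception before day 0 that the single screening test missed: conception on day −44 gives a 37-week birth on day 201.

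**Step 4: do later contacts fill the gap?** Counted from day 180, Visit 3 falls between 180 + 60 = day 240 and 180 + 180 = day 360. It could therefore meet some births if she is still in the study. Counted from an early stop it falls sooner: after a stop 28 days past conception, it comes 88 to 208 days after conception, before term. Sections 6.1.1, 8.1 and 8.2 describe Visit 3 as asking about gentamicin use and UTIs. The optional survey window runs to 180 + 90 + 365 = day 635, past the latest term birth, but the survey covers perceptions and satisfaction. Either contact could bring an outcome to light; neither is set up to ask for it.

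**The case against.** The strongest reply is that only the conflict between 2.3.1 and 8.3.9 is established, and that it is a drafting slip. The rest depends on documents outside the text reviewed. Consent pages were removed, section 10.1.8 leaves full procedural detail to the Manual of Operations, and section 8.3.5 defers to IRBMED guidance. Any of these may already require pregnancy follow-up. That objection stands, and it is why the outcome check is put forward only conditionally.

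A reader might infer from 8.3.4 that a birth defect found after day 210 need not be reported. The documents do not support that. Section 8.3.6 sets no end date, so a defect learned of through record review, Visit 3, the survey contact or the participant would still be reportable. The possible gap is in looking, not in the duty to report.

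A reader might also infer that nobody would be watching. For a participant who stays, that is too strong. Calls, record reviews and health updates continue, and a pregnancy already on file would be a natural topic. These contacts could also reveal an early loss. This strengthens the main point, since 8.3.9 is what would take them away.

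Finally, the numbers will be tiny. There is a screening test, required contraception, bi-weekly questions and mandatory stopping, in a trial that aims to retain at least 15 participants of both sexes. Section 2.3.1 reports no detectable serum gentamicin in the human tests. All of that stands and keeps the severity low.

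**Conclusion.** The conflict holds without any outside assumption: 2.3.1 and 8.3.9 give opposite instructions on participation, and no other section resolves them. Sections 2.3.1 and 7.1 agree with each other, so 8.3.9 is the one to change.

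The outcome gap holds only if the Manual of Operations, consent form and IRBMED rules do not already fill it. Its size is at least 56 days between the end of routine AE collection and any term birth conceived on treatment. That figure rests on 266 days from conception and on treatment ending by day 180. The number of such pregnancies cannot be estimated from the documents and is expected to be very small. Neither the primary analysis nor any other efficacy result is affected. Severity: minor.

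**What to change.** **Main change.** Reword 8.3.9 so that a participant reporting a new pregnancy *will discontinue study treatment and, if willing, remain in the study for follow-up*. This matches 2.3.1 and 7.1 and leaves mandatory stopping of the drug as it is. It costs one sentence and the IRB review that any amendment needs.

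**Conditional addition.** First check the Manual of Operations, consent form and IRBMED rules. If they already cover pregnancy outcome, cite the source in 8.3.9 and stop there. If not, add to 8.3.9 one participant contact and record check around the due date, with consent, for any pregnancy exposed to study product, and report any congenital anomaly under 8.3.6. The cost is a short consent amendment, a decision on re-consenting those already enrolled (Statement of Compliance), and one extra contact for a rare participant. Her record would stay open 56 to 236 days longer on the arithmetic above, and the outcome may rest on her own report if she delivers outside Michigan Medicine.

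**If treatment is already complete.** The SAP of June 2023 is largely in the past tense, so this may be the case. An amendment would then protect nobody still on drug. Instead, check the bi-weekly call records for any pregnancy and, if there was one, ask for its outcome with consent.
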